**Study Title**

Vitamin D and Vascular Function in Obese Children

**Objectives**

The primary objective of this randomized clinical trial is to determine the efficacy of enhanced vitamin D3 supplementation in improving vascular endothelial function, arterial stiffness, insulin sensitivity, and metabolic syndrome risk status in 10- to 18-year-old vitamin D-deficient (serum 25-hydroxyvitamin D <20 ng/mL) obese or overweight (BMI  $\geq 85^{\text{th}}$  percentile) children; and to assess whether these effects are dose-dependent. As a secondary objective, we will examine the vitamin D supplementation-induced effect on adipokines and inflammatory markers relevant to CVD risk.

**Design and Outcomes**

In a double-blinded, controlled trial, we propose to randomize 229 eligible children to receive either 600 IU (conventional supplementation, current recommended dietary allowance), or 1000 IU or 2000 IU (enhanced supplementation) of vitamin D3 daily for six months.

The primary outcome measure will be change in brachial flow-mediated dilation percentage at 6 months (FMD%); FMD% is a measure of vascular endothelial function. The secondary outcome measures will include (1) pulse-wave velocity (PWV) – a measure of arterial stiffness, (2) central and systemic blood pressure, (3) fasting blood glucose concentration, (4) 1/fasting insulin concentration as a surrogate for insulin resistivity, (5) lipid profile indices, (6) adipocytokines (plasma leptin, and adiponectin) and systemic markers of inflammation (plasma high-sensitivity CRP, IL-6, TNF- $\alpha$ ).

Eligible participants will be scheduled for enrollment within eight weeks of the initial screening visit. Follow-up visits will occur approximately at three months and six months after enrollment. FMD%, PWV, biochemical measurements, and inflammatory markers will be obtained at each study visit; DXA scan will be done at enrollment and at 6 months.

**Interventions and Duration**

Enrolled children will receive daily oral supplementation of either 600 IU or 1000 IU or 2000 IU of vitamin D3 for six months.

**Sample Size and Population**

We aim to enroll 229 otherwise healthy 10- to 18-year-old, overweight (BMI percentile,  $\geq 85^{\text{th}}$  to  $< 95^{\text{th}}$ ) or obese (BMI percentile,  $\geq 95^{\text{th}}$ ), vitamin D-deficient (serum 25(OH)D concentration <20 ng/mL) children.

## 1. **STUDY OBJECTIVES**

### 1.1 Primary Objective

To determine whether enhanced vitamin D3 supplementation in 10- to 18-year-old obese and overweight children with serum 25(OH)D <20 ng/mL results in: (a) improved vascular health (arterial endothelial function and arterial stiffness) and (b) improved insulin sensitivity and metabolic syndrome markers (blood pressure, fasting blood glucose, lipid profile). We hypothesize that vitamin D3 supplementation with 2000 IU or 1000 IU daily will be more effective than 600 IU in improving vascular health and insulin sensitivity and metabolic syndrome markers.

### 1.2 Secondary Objectives

To examine whether downregulation of systemic inflammatory markers and adipokines underlie the effects of vitamin D on vasculature and metabolism. We hypothesize that vitamin D effects on vascular health and metabolism may be driven by the attenuation of obesity-associated inflammation.

## 2. **BACKGROUND AND RATIONALE**

### 2.1 Background on Condition, Disease, or Other Primary Study Focus

Childhood obesity is a major public health problem in the United States (US). In 2007-2008, 32% of 2- to 19-year-old US children were either obese (BMI  $\geq 95^{\text{th}}$  percentile) or overweight (BMI 85th - 94th percentile). Obese and overweight children exhibit cardiovascular disease (CVD) risk factors and have a high risk of metabolic syndrome (i.e. large waist circumference, hypertension, fasting hyperglycemia, hypertriglyceridemia, and low levels of high-density lipoprotein (HDL) cholesterol). Obesity and its atherogenic risks track from childhood to adulthood, increasing the risk of adult CVD and pointing to the need for developing primary prevention strategies in affected children.

### 2.2 Study Rationale

Vitamin D deficiency is emerging as an independent risk factor for CVD and metabolic syndrome in children and adults. Our preliminary work shows that obese children have an increased risk of vitamin D deficiency; hypovitaminosis D is also associated with other CVD risk factors, such as low HDL cholesterol and lower insulin sensitivity in youth. Accordingly, optimization of vitamin D status in obese children might improve their CVD risk profile and reduce their risk of later CVD. As vitamin D is a potent immune modulator, its cardiovascular and metabolic benefits might be mediated, in part, through downregulation of inflammatory mediators, including adipokines.

In the proposed study, we will test the central hypothesis that enhancement of vitamin D status in otherwise healthy obese and overweight vitamin D-deficient children will improve their vascular health and their CVD and metabolic syndrome risk profile.

### **3. STUDY DESIGN**

We propose a double-masked, randomized, controlled clinical trial of enhanced vitamin D3 supplementation (600 IU vs 1000 IU vs 2000 IU) for six months in 10- to 18-year-old, overweight (BMI percentile,  $\geq 85^{\text{th}}$  to  $< 95^{\text{th}}$ ) or obese (BMI percentile,  $\geq 95^{\text{th}}$ ), vitamin D-deficient (serum 25(OH)D concentration  $< 20$  ng/mL) children. Children who seek care at the Primary Care Centers of CHP (Oakland, Mercy Hospital, and Turtle Creek) or at affiliated PittNet offices (Practice Based Research Network, PBRN) will be eligible to participate. Our primary aim is to determine whether enhanced supplementation with vitamin D3 (1000 IU or 2000 IU) compared to the standard of care vitamin D3 supplementation (600 IU), taken orally once daily, is effective in improving brachial FMD% by 25% or more at the end of six months. Secondary outcomes will determine effects of vitamin D supplementation in reducing arterial stiffness, improving insulin sensitivity, and reducing metabolic syndrome risks. We will also characterize the mechanistic effects of vitamin D on systemic inflammatory markers and adipokines relevant to CVD risk.

### **4. SELECTION AND ENROLLMENT OF PARTICIPANTS**

Children who seek care at the Primary Care Center of CHP Oakland or at affiliated PittNet offices (Practice Based Research Network, PBRN) will be eligible to participate.

*Eligible children will meet the following inclusion and exclusion criteria*

#### **4.1 Inclusion Criteria**

Potentially eligible children will be

- 10 to 18 years of age
- otherwise healthy
- obese or overweight (BMI  $\geq 85^{\text{th}}$  percentile)
- able to understand all aspects of study procedures
- able to voluntarily comply with all study procedures across the duration of the study
- vitamin D-deficient and normocalcemic during screening (serum 25(OH)D concentration  $< 20$  ng/mL; serum calcium concentration: 10-14 years, 8.8-10.8 mg/dL;  $\geq 15$  years 8.4-10.2 mg/dL)

#### **4.2 Exclusion Criteria**

Children will be excluded from the study if they meet any of the following exclusion criteria:

- Have hepatic or renal disease, metabolic rickets, malabsorptive disorders, primary hyperparathyroidism, hyperthyroidism, previous history of cancer or other chronic disorders that could affect vitamin D or glucose metabolism
- Are receiving treatment with anticonvulsants, systemic glucocorticoids, pharmacologic doses of vitamin D ( $\geq 1000$  IU of vitamin D2 or D3 daily), antihypertensives, vasoactive drugs, antilipidemics, metformin, antipsychotics, other oral insulin regulators, or cancer treatments
- Have cholelithiasis or urolithiasis

- Have type 1 or type 2 diabetes
- Have a condition or underlying abnormality that could compromise the safety of the subject during study procedures (e.g. sickle cell trait/disease)
- Found to be hypercalcemic during screening visit (serum calcium  $>10.8$  mg/dL in 10- to 14-year-old children;  $>10.2$  mg/dL in  $\geq 15$ -year-old children)
- Significant fasting hyperglycemia (fasting blood glucose concentration  $\geq 125$  mg/dL) during the enrollment visit
- Post-menarchial girls with a positive pregnancy test at enrollment will be excluded; however, contraception is not required for post-menarchial girls

#### **4.3 Study Enrollment Procedures**

Participants will be recruited from the Primary Care Center of CHP Oakland or at affiliated PittNet offices. In addition to the two recruitment locations, participants may also be recruited through various community outreach programs. The study will also be advertised through the University of Pittsburgh Pitt+Me database to strengthen our recruitment effort.

Potential participants among children attending the CHP Oakland Primary Care Center will be screened for eligibility by reviewing their EPIC electronic medical records. Subjects who are not excluded during the preliminary EPIC chart review will be approached for screening. Reasons for inclusion and exclusion will be electronically documented on a screening form in the study-specific electronic database administered by the University of Pittsburgh Center for Research on Health Care (CRHC).

Written informed consent from a biological or legally-adoptive parent and participants' assent, will be obtained prior to enrollment (both screening and enrollment) of 10- to 17-year-old children. Participants who are 18 years of age can consent for themselves for both screening and enrollment. Legal guardians will have to provide documentation of guardianship from relevant agencies and/or courts.

Participants found to be vitamin D-deficient during screening, and thus eligible for study enrollment, will be randomized to one of three vitamin D supplementation doses (600 IU, 1000 IU, or 2000 IU). The randomization codes will be assigned electronically through the CRHC study database using a block randomization scheme set forth by the study statistician prior to the onset of the study. Both participants and study investigators will be blinded to the assigned supplementation dose throughout the trial.

### **5. STUDY INTERVENTIONS**

#### **5.1 Interventions, Administration, and Duration**

Enrolled study participants will be randomized to one of three vitamin D supplementation doses: 600 IU (conventional supplementation), 1000 IU, or 2000 IU (enhanced supplementation). Assigned study vitamin D supplement bottle will be dispensed to the participants at enrollment and 3-month follow-up visit. Supplementation bottles will be given with Medical Event Monitoring System caps (MEMS, manufactured by AARDEX Group Ltd., Sion, Switzerland) for assessing and enhancing adherence. Participants will be instructed to take only one study vitamin D tablet daily for the duration of the study, and to not double their dose if a

previous dose was missed.

## 5.2 Handling of Study Interventions

Study vitamin D supplements will be manufactured by Douglas Laboratories in Pittsburgh, PA. The procurement of the required tablets will be coordinated in conjunction with the UPMC Investigational Drug Service Research Pharmacist. Study vitamin D supplements will be directly shipped to the research pharmacist who will ensure appropriate masking, labeling, bagging, and coding of the supplement bottles. The study vitamin D supplements will be identical in color, taste, and size. Each dispensed bottle will contain 105 pills.

The coded study vitamin D supplement bottles will be stored in a locked cabinet in the UPMC Osteoporosis Prevention and Treatment Center in the Kauffman Building. Once, the trial is completed, all excess vitamin D supplements will be returned to the UPMC Investigational Drug Service research pharmacist for discarding.

If multiple children of the same household enter the study, the dispensed supplement bottles will be color-coded to ensure identification of their respective medication.

## 5.3 Concomitant Interventions

### Allowed Interventions

For the duration of the study, participants are permitted to take any medications that are not included in the list of prohibited interventions.

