### Prohibited Interventions

Participants are expected to not take the following medications during their participation in the study. If these medications are clinically necessary and prescribed by a provider, the participant may be withdrawn from the study based on the PI's discretion.

- Multivitamins
- Anticonvulsants
- Systemic glucocorticoids
- Antipsychotics
- Antihypertensives
- Vasoactive drugs
- Antilipidemics
- Metformin or other oral insulin regulators
- Chemotherapeutics or other cancer treatments

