## **Screening**

The following procedures are performed to determine a subject's eligibility:

- *Age Calculation:* To enter the study children should have completed their 10th birthday and not have had their 19th birthday. 18-year-old children are eligible to enroll until the day before their 19th birthday.
- *BMI Calculation:* Height will be measured three times in centimeter (cm) to the nearest 0.1-cm and averaged to determine the participant's height in centimeter. Weight will be measured three times in kilogram (kg) to the nearest 0.1-kg and averaged to determine the participant's weight in kilogram. BMI will be calculated using the following formula:

$$[\text{Weight in kilogram}]/[\text{Height in meter}]^2$$

BMI can also be calculated using metric measurements of height (in cm) and weight (in kg) through NHLBI online BMI calculator available at:

<http://nhlbisupport.com/bmi/bminojs.htm>

- *Medical History Form:* Captures anthropometrics, demographic data (age, sex, race, and ethnicity), level of education, smoking status, current medications, and type of medical insurance.
- *Contact Form:* To be completed by parent unless subject is 18 years of age
- *Vitamin D and Sunlight Exposure Questionnaire:* To be completed by parents unless subject is 18 years of age
- *Waist Circumference Measurement:* Waist circumference will be measured three times, using a non-stretch tape measure, at the mid-point between the lowest rib and the iliac crest at minimal respiration while standing. The respective waist circumference measurements will be measured to the nearest 0.1 cm and averaged.
- *Fitzpatrick Sun-reactive Skin Type estimation:* Sun-reactive skin type estimate will be made by the parent unless the subject is 18 years of age
- *DSM II Colormeter Measurement:* Study staff will normalize the dermatophotopspectrometer on the calibration plate and obtain three readings from the forehead, back of the hand, and inner upper arm. The measurements obtained at each site will be averaged to estimate the melanin index at the respective sites.
- *Venipuncture, Specimen Collection, and Specimen Processing:*

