### 9.2 Sample Size and Randomization

Our sample size estimates are based on showing a relative improvement in baseline brachial artery flow mediated vasodilation (FMD, %) of at least 25% in children receiving each of the higher doses of vitamin D3 (1000 IU and 2000 IU) compared with no improvement in the 600 IU group after six months of treatment. We assumed the baseline FMD was ~6.5% based on previous studies in overweight children similar to our projected population. A sample size of 56 in each treatment group at the end of the trial would have 84% power (two-sided two-sample comparison of means,  $\alpha=0.025$ ) to detect this clinically important difference of 25% relative improvement (absolute improvement=25%\*6.5%≈1.6%) assuming a standard deviation of 2.6% (conservative estimates based on published literature). To provide for a projected drop-out rate of 25% by the end of the trial, we propose to recruit 225 children into the trial. We have over 90% power to detect a dose-response effect by testing for linear trend assuming a 0%, 20%, and 30% improvement in vascular health among children receiving 600 IU, 1000 IU, and 2000 IU, respectively.

Our original sample size of n=252 was based on 90% power and 20% attrition to allow for subgroup analyses by race. In December of 2015, the PI and funder decided to re-evaluate the targeted sample size due to slower than expected recruitment. Accordingly, with approval from NHLBI, our accrual target was revised from 252 participants to 229 participants based on projected enrollment and power of at least 80% to detect the original effect size with 25%-30% attrition. The lower sample size of n=225 would still allow for detection of clinically significant effect of vitamin D supplementation. However, the proportion of African Americans in the recruited sample was much larger than anticipated; the small number of Caucasian subjects in the cohort precludes doing race-stratified analysis. For the secondary outcomes, we have 89% power to detect effect sizes of 0.61 or greater without adjustment for multiplicity.

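### Section 5.3 bars multivitamins but not stand-alone vitamin D, so children may take the test agent open-label, which risks diluting the dose contrasts toward the null

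*Combined protocol and SAP*

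**What the plan says.** Under Allowed Interventions, section 5.3 sets a default: "participants are permitted to take any medications that are not included in the list of prohibited interventions". Prohibited Interventions then opens with "Participants are expected to not take the following medications during their participation in the study" and gives nine lines: multivitamins, anticonvulsants, systemic glucocorticoids, antipsychotics, antihypertensives, vasoactive drugs, antilipidemics, metformin or other oral insulin regulators, and cancer treatments. If a provider prescribes one of these, withdrawal is at the PI's discretion. Vitamin D by itself is not on the list.

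Section 4.2 does exclude, at entry, children who "Are receiving treatment with anticonvulsants, systemic glucocorticoids, pharmacologic doses of vitamin D", where pharmacologic means 1000 IU or more of D2 or D3 a day. Section 5.1 adds "Participants will be instructed to take only one study vitamin D tablet daily for the duration of the study". Section 4.1 requires that children be "vitamin D-deficient and normocalcemic during screening", with 25(OH)D below 20 ng/mL.

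**The concern.** The trial compares three doses of vitamin D, and the lower contrast is only 400 IU wide (1000 minus 600). A child in the 600 IU arm who adds a 400 IU product takes the middle arm's daily dose. The protocol evidently meant to limit outside vitamins, since it added multivitamins to the on-study list although section 4.2 does not name them. Yet the rule that anything unlisted is allowed leaves the test agent itself permitted.

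Masking makes differential use between arms unlikely. What is at stake is a smaller true difference between arms than the one the trial was sized for, and so a higher chance of missing a real effect.

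**Working it through.** **Does any other text close the gap?** Section 4.2 excludes ten treatments: anticonvulsants, systemic glucocorticoids, vitamin D at 1000 IU or more, antihypertensives, vasoactive drugs, antilipidemics, metformin, antipsychotics, other oral insulin regulators, and cancer treatments. Nine recur in section 5.3, with metformin and the other insulin regulators sharing a line. Only vitamin D is missing.

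- Section 4.2 applies at entry only, and leaves doses under 1000 IU open even then.
- Section 5.1 and Required Interventions govern the study tablet.
- Section 5.4 (MEMS cap, pill count, calendar) tracks the study supplement.
- The medical history form ("smoking status, current medications, and type of medical insurance"), the vitamin D questionnaire at screening and 6 months, and the DSMB listing of off-protocol treatments (section 9.3) may record outside use but do not forbid it.

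Nothing closes the gap.

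**Plan's own figure.** Inputs from section 9.2: n = 56 per arm, SD 2.6, two-sided α = 0.025, difference 25% × 6.5 ≈ 1.6 points. Standard error = 2.6 × √(2/56) = 0.491, and noncentrality = 1.6/0.491 = 3.26 on 110 df. Noncentral-t power is 83.6%, matching the stated 84%.

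**Dilution.** Assumed, because the documents give no rate or dose: a share p of every arm takes an extra 400 IU daily throughout. Each comparison is set to 1.6 points without outside use, as section 9.2 does.

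- Linear response: outside use shifts all arms equally, so the difference stays 1.6.
- Log-dose response: d = (1−p) × 1.6 + p × 1.6 × ln((D+400)/1000)/ln(D/600). The ratio of logs is 0.336/0.511 = 0.659 for D = 1000 and 0.875/1.204 = 0.727 for D = 2000.
- Plateau from 1000 IU: a user in the 600 IU arm gains the full effect and users in the other arms gain nothing, so d = (1−p) × 1.6.

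| Response | Comparison (IU) | p = 10%: d, power | p = 20%: d, power |
|---|---|---|---|
| Linear | both | 1.60, 84% | 1.60, 84% |
| Log-dose | 1000 vs 600 | 1.545, 81% | 1.491, 78% |
| Log-dose | 2000 vs 600 | 1.556, 81% | 1.513, 79% |
| Plateau | both | 1.44, 74% | 1.28, 63% |

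**The curve in section 9.2.** For the trend test only, the plan sets power "assuming a 0%, 20%, and 30% improvement in vascular health among children receiving 600 IU, 1000 IU, and 2000 IU, respectively". On a 6.5% baseline that is 0, 1.30 and 1.95 points. Take it as linear between doses and, above 2000 IU, either flat or continuing at 0.65 points per 1000 IU. With p = 20%:

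- 600 IU arm: 0.2 × 1.30 = 0.26.
- 1000 IU arm: 1.30 + 0.2 × 0.26 = 1.352. Difference from 600 IU: 1.092, down 16% from 1.30.
- 2000 IU arm: 1.95 (flat) to 2.002 (continuing). Difference from 600 IU: 1.690 to 1.742, down 13% to 11% from 1.95.
- Trend contrast (−1, 0, 1), 165 df, α = 0.05: power 97.6% with no outside use, 92.8% to 94.1% with it. This still meets the stated figure of over 90%.

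**The case against.** The strongest reply is that the size rests on invented inputs. The documents give no rate or dose of outside use, and +400 IU is exactly the 600-to-1000 gap, which makes the plateau case as bad as it can be. With a linear rise from 600 to 1000 IU and a flat response above, +200 IU gives d = 1.52 and 79% power at 10% use, and d = 1.44 and 74% at 20%. At 5% use, power is 79% with +400 IU and 82% with +200 IU. Use that starts late in the six months would count for less again. This stands: the figures illustrate a range and do not predict.

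The log-dose rows set both comparisons to 1.6 points, which no single log curve can do: one giving 1.6 at 1000 IU gives 3.8 at 2000 IU. That is also true. Each row should be read as one comparison on its own, which is how section 9.2 states its power.

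Existing data collection would help reveal outside use, and families may have been told more in consent material or an operation manual that is not available here. Recording is not prohibition, though, and under section 5.3 such use would not even be off-protocol. The low 25(OH)D required at entry plausibly makes effective supplementation less common at the start, but it does not limit later use.

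Finally, section 9.2 shows recruitment well under way by December 2015, so a change would reach only children still on treatment. Withdrawals also cost power: losing 10% per arm (56 to 50) would give 79% at 1.6 points. That is an upper-bound illustration, since withdrawal is discretionary and would concern only prescribed users.

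**Conclusion.** The concern holds. The wording of section 5.3 permits non-study vitamin D during a trial of vitamin D dose, and no other section forbids it. The consequence is a risk of dilution toward the null; with masked arms there is no reason to expect differential bias, and the gap would not manufacture a positive result. Its size is unknown. For 10% to 20% of every arm taking +400 IU daily, the loss of power per comparison ranges from none (linear response) to about 20 percentage points (84% to 63%, plateau with 20% use). Which comparison suffers more depends on the curve: they are nearly equal under the log-dose assumption, equal under the plateau, and 1000 vs 600 IU is proportionally worse under the 0/20/30% curve. Section 9.2 had already cut the sample to a floor of at least 80% power, so there is little reserve. This is a gap worth closing, not a fatal flaw.

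**What to change.** Add to the prohibited list in section 5.3: non-study vitamin D (D2 or D3), alone or combined with calcium, under the PI-discretion rule already there for provider-prescribed use. Leave the intention-to-treat analysis in section 9.5 unchanged. Optionally, summarise outside vitamin D use by arm from the medical history forms already completed at 3 and 6 months; no new form is needed.

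The cost is one line of text. Families would have to stop outside vitamin D while every child receives at least 600 IU, which the protocol gives as the current recommended allowance. A few children prescribed vitamin D might be withdrawn at the PI's discretion.
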